## Mode of delivery (CS/vaginal)(E):

- Information will be obtained from the DPP (FIN), MBR (SWE, NOR).

## Preterm birth (E):

- Information on gestational age will be obtained from the DPP (FIN) and MBR (SWE, NOR). Preterm birth is defined as length of gestation less than 37 completed GW.

## Birth height (E):

- Information will be obtained from the DPP (FIN) and MBR (SWE, NOR). LBH is defined according to national standards in each country as available (FIN: Sankilampi et al. 2013).

## Birth weight (E):

- Information will be obtained from the DPP (FIN) and MBR (SWE, NOR). LBW (E) is defined as birth weight less than 2500 grams. High birth weight is defined as 4500 grams or more.

## Birth weight for gestational age (E):

- Information will be obtained from the DPP (FIN) and MBR (SWE, NOR). It is defined according to the gestational age and sex-specific national standards in each country as available (FIN: Sankilampi et al. 2013). AGA is used as reference outcome in relation to SGA and LGA.

## Sex of the newborn (E):

- Information will be obtained from the DPP (FIN) and MBR (SWE, NOR)

## Head circumference (E):

- This information will be obtained from the DPP (FIN) and MBR (SWE, NOR) and is measured as centimetres. Low head circumference is defined according to national standards in each country as available (FIN: Sankilampi et al. 2013).

## Apgar scores (E):

- These are registered at 1 and 5 minutes after birth. Low Apgar score is defined as less than 7 in 1-minute and 5-minutes score. Information is available from the DPP (FIN) and MBR (SWE, NOR).

## Any chronic diseases:

- Information on chronic diseases available from the DPP (FIN), MBR (FIN, SWE, NOR), MS Register, Patient Register (SWE, NOR), Prescription Register (FIN, SWE, NOR) will be used to define pharmacological treatment for comorbidities. The comorbidities listed in Table 4 existing before, or during pregnancy will be identified based on diagnoses or specific medications for chronic diseases. These represent the most common chronic diseases among women who have been pregnant (information source the DPP, years 1996-2010). Information is based on pre-pregnancy diagnoses. From these comorbidities a binary variable will be created to indicate if the mother has had any chronic diseases before or during pregnancy (Yes, No). Lifetime pre-pregnancy diagnoses are included from the time period included in the data sources.

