**Table 2: List of relevant data sources in different countries.**

Finland		
Outcome	Register	Register holder
Ectopic pregnancies	Patient Register (Care Register for Health Care)	National Institute for Health and Welfare (THL)
Spontaneous abortions	Patient Register (Care Register for Health Care) (of previous pregnancies from DPP)	THL
Elective terminations	DPP	THL
Stillbirths with and without foetal defects	DPP	THL
Live births with and without congenital anomaly	DPP	THL

Exposure	DPP National Prescription Register National Reimbursement Register	THL Social Insurance Institution (SII)
MS population	DPP, Patient Register (Care Register for Health Care)	THL
General population	Population Register	Statistics Finland (SF)
Sweden		
Outcome	Register	Register holder
Ectopic pregnancies	Patient Register	National Board of Health and Welfare
Spontaneous abortions	Patient Register	National Board of Health and Welfare
Elective terminations	not recorded in SWE	N/A
Stillbirths with and without foetal defects	MBR	National Board of Health and Welfare
Live births with and without congenital anomaly	MBR	National Board of Health and Welfare
Exposure	Prescribed Drug Register	National Board of Health and Welfare
MS population	Patient Register, MS Register	National Board of Health and Welfare
General population	Population Register	Swedish Tax Agency
Norway		
Outcome	Register	Register holder
Ectopic pregnancies	Patient Register	Norwegian Directorate of Health
Spontaneous abortions	Patient Register (of previous pregnancies in MBR)	Norwegian Directorate of Health Norwegian Institute of Public Health (NIPH)
Elective terminations	MBR	NIPH
Stillbirths with and without foetal defects	MBR	NIPH
Live births with and without congenital anomaly	MBR	NIPH
Exposure	Prescription Register	NIPH
MS population	MS Register	Helse Bergen
General population	Population Register	Statistics Norway

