#### **Register on Reimbursed Medications (FIN)**

In FIN, information on chronic diseases can be obtained from the separate register on special medical reimbursements for treatment of chronic disease. Information on maternal MS diagnoses obtained from the DPP (FIN) is based on this Register on Reimbursed Medications maintained by the SII of Finland. All the patients who are entitled for special reimbursement due to MS diagnosis are included in the register. Reimbursement for MS requires a medical certificate demonstrating that the diagnosis is based on clinical examinations, fulfils international criteria, and is made by a board-certified physician. The medical certificate is issued when the MSDMD treatment is started.

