### **Patient Registers (FIN, SWE, NOR)**

Information on hospitalisations due to MS, spontaneous abortions, and ectopic pregnancies will be obtained from the Patient Registers in this study. The Patient Register includes individual-level inpatient data in FIN SWE and NOR (established: FIN 1969, SWE 1987, NOR 2008). Outpatient visits are available since 1998 in FIN, 2001 in SWE and 2008 in NOR. The registers include data on hospitalisations with information on diagnosis (ICD-10), start and end date of the hospitalisation period, operations and other procedures performed, and identification of the hospital and the hospital district. In addition, outpatient visits in the secondary healthcare units and day surgeries are included the registers. No primary care data are currently available.

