**Table 4: List of chronic diseases diagnosed before LMP and during pregnancy.**

Comorbidities	ICD-10	Proportion of women with the disease among parturient (%) in Finland 1996-2010 
Asthma and related conditions	E84.0, J41–J45, P27.1	2.77
Hypothyroidism (thyroid insufficiency)	C73, E03, E89.0	0.82
Epilepsy	C71, G40, G41	0.80
Rheumatoid arthritis and related conditions	A04.6, A39.8, A50.5, D76.0, D76.3, H20.1, H30, I33.0, J84, K50.9, K51.9, K73.2, K74.3, K83.0, L40.5, M02, M05, M06, M08, M13.9, M30–M35, M45, M46.1, M46.9, M94.1, N03, Q44.2	0.61
Diabetes Mellitus (type I and type II will be considered separately)	E10–E14, E89.1	0.52
Colitis Ulcerosa, Crohn's disease	K50, K51	0.50
Hypertensive diseases	I10–I13, I15, I27.0	0.38
Severe psychosis and other severe mental disorders and related conditions	A52.1, A69.2, A81.0, B22.0, B56.9, B57.2, E01.8, E03.9, E52, E53.8, E75.6, E83.0, E83.5, F01, F03, F06.0–F06.3, F20–F25, F28, F29, F30.1, F30.2, F31, F32.3, F33.3, F84, G10, G20, G30.0, G30.1, G30.8, G30.9, G31.0, G35, G40.9, M30.0, M32.8	0.32
Leukaemia and related conditions	C81–C85, C88, C90–C96, D45–D47, D72.1, D75	0.06
Hypercholesterolemia and mixed hyperlipidemia	E78.0, E78.2	0.05
Hypogonadism	E28.3, E29.1, E89.4, E89.5, Q96, Q98	0.04
Hypertensive heart disease with heart failure and related conditions	I11.0, I13, I50, I97.1, P29.0	0.04
Chronic arrhythmia of the heart	I47–I49	0.04
Glaucoma	H40	0.03
Pernicious anemia and deficiency of specified B group vitamins	C16, D51, E53.8	0.03

Comorbidities	ICD-10	Proportion of women with the disease among parturient (%) in Finland 1996-2010 
Hypothyroidism parathyroid gland, chronic (parathyroid insufficiency)	E20, E31.0, E89.2	0.02
Deficiency of coagulation, hemophilia	D66, D67, D68.0–D68.2	0.01
Myasthenia gravis	G70.0	0.01
Maternal pregnancy-related disorders	O10-O29	not available from DPP
Other malignancies	C00-C80	not available

Lahesmaa-Korpinen et al. 2014

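### The chronic-disease covariate omits the Finnish Patient Register, a source the study already uses, so unreimbursed hospital diagnoses can be missed in 46.5% of planned pregnancies

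*Protocol*

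**What the plan says.** Section 9.4, under any chronic diseases, opens its list of sources with the DPP: "Information on chronic diseases available from the DPP (FIN"). It continues with "MBR (FIN, SWE, NOR), MS Register, Patient Register (SWE, NOR), Prescription Register (FIN, SWE, NOR"). The birth register and the Prescription Register carry all three countries; the Patient Register carries two. A comorbidity may be identified from a diagnosis or from a specific medication, and lifetime diagnoses before pregnancy count as far back as each source reaches. The result is one yes/no variable.

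Elsewhere the Finnish Patient Register is a study source. Table 2 gives the source for the Finnish MS population as "DPP, Patient Register (Care Register for Health Care"), and lists the same register for ectopic pregnancies and spontaneous abortions. Section 9.3.1.2 says "The Patient Register includes individual-level inpatient data in FIN SWE and NOR". It dates the Finnish register to 1969, with outpatient visits from 1998, and says that the registers hold ICD-10 diagnoses.

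For Finland, section 9.3.1.1 says that "information on chronic diseases can be obtained from the separate register on special medical reimbursements for treatment of chronic disease". That register feeds the DPP. The DPP's description lists the birth, induced-abortion and malformation registers plus drug purchases and reimbursements. The Patient Register is not among them.

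Section 9.7.3 puts the variable in the base model as an a priori confounder.

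**The concern.** If the same disease is detected by different routes in different countries, one pooled coefficient is fitted to a variable that does not mean the same thing everywhere. A country main effect shifts the baseline risk. It does not repair a covariate whose sensitivity differs between countries or within one.

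There is a second element. The primary denominator in Table 6 is elective terminations plus births. Finnish terminations come from the abortion register through the DPP and have no birth record for that pregnancy. A disease that would be known only from that record is visible for a birth and invisible for a termination. Terminations for foetal anomaly are part of the primary composite, so measurement of a confounder is tied in part to the outcome. What is at stake is some residual confounding in the primary RR that a source already in the study could reduce.

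**Working it through.** **1. Finland's share (section 9.5).** 433 + 4 × 86 = 777; Sweden 329 + 3 × 51 = 482; Norway 330/0.8 = 412. The total is 1671, as stated. 777/1671 = 46.5%.

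**2. Routes by which a Finnish Table 4 disease can be seen.**

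| Route | Tied to how this pregnancy ended? |
|---|---|
| Special reimbursement (via DPP) | No |
| Reimbursed drug purchase | No |
| Birth register, earlier birth | No |
| Birth register, this pregnancy | Yes, births only |
| Patient Register | Not listed for Finland |

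A hospital diagnosis that is untreated or unreimbursed and has no earlier birth record is seen only through the fourth row. That is the gap.

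**3. Possible size.** The Protocol gives neither the capture of the Finnish sources nor the imbalance between cohorts, so these inputs are assumptions:

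- disease prevalence 10–20% in exposed and 7–10% in unexposed pregnancies (the 18 quantified rows of Table 4 add to 7.05%, an upper bound on any listed disease among Finnish parturients if rows overlap);
- RR of disease on outcome 1.3–2.0, and outcome risk 6% without disease;
- sensitivity 40–80%, specificity 1, capture unrelated to outcome;
- true exposure RR 1.00; cohort sizes in the planned ratio 294 to 1270.

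The Mantel-Haenszel RR over the recorded covariate is Σ(a·n0/N) / Σ(b·n1/N), where a and b are exposed and unexposed events, n1 and n0 the group sizes and N their sum, by stratum. The least favourable corner (20% against 10%, disease RR 2.0, sensitivity 40%) gives:

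- recorded yes: n1 = 294 × 0.20 × 0.4 = 23.52, a = 23.52 × 0.12 = 2.822; n0 = 1270 × 0.10 × 0.4 = 50.8, b = 50.8 × 0.12 = 6.096;
- recorded no: n1 = 270.48, a = 35.28 × 0.12 + 235.2 × 0.06 = 18.346; n0 = 1219.2, b = 76.2 × 0.12 + 1143 × 0.06 = 77.724;
- numerator 1.929 + 15.015 = 16.944; denominator 1.929 + 14.112 = 16.041; RR = 1.056.

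With no adjustment the RR is 1.20/1.10 = 1.091. The most favourable corner (10% against 7%, disease RR 1.3, sensitivity 80%) gives 1.002.

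A second set of assumptions (25–30% against 20%, disease RR 1.5–2.0, sensitivity 30–50%) gives 1.013–1.062 adjusted and 1.023–1.083 crude.

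These factors apply within Finland. If the other two countries carried no residual bias and Finland's weight were its share of pregnancies, the pooled excess would be about 0.465 × 0.056 = 0.026, an RR near 1.03. The plan's minimum detectable RR for cohort 1 against cohort 3 is 1.72.

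**4. Not modelled.** Outcome-dependent capture is not in this calculation. Terminations for foetal anomaly are events and terminations for other reasons are non-events in the same denominator, so the direction cannot be fixed from the Protocol.

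**The case against.** The best defence is that Finland has good alternatives. Special reimbursement for MS needs a medical certificate, and the Prescription Register holds all reimbursed purchases, not only those under special reimbursement. Both count whatever the pregnancy outcome, and lifetime look-back admits earlier birth records. This stands. It rules out the stronger reading that Finnish diseases without special reimbursement are seen only when the pregnancy ends in birth.

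A reader might also count spontaneous abortions and ectopic pregnancies as evidence of bias in the primary RR. They are outside its denominator in Table 6, so they matter only for the secondary comparisons.

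Nor is there a uniform Swedish and Norwegian variable from which Finland departs: the Norwegian Patient Register starts in 2008 and the Norwegian study period in 2004.

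Table 4's entry "not available from DPP" might be read as proof of non-capture. It stands in the column of Finnish proportions and shows only that no figure was available.

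Sections 9.4 and 9.7.1 use confounders according to availability. That does not explain the omission, because the register is available. However, section 9.3.1.2 states a narrower use: "Information on hospitalisations due to MS, spontaneous abortions, and ectopic pregnancies will be obtained from the Patient Registers in this study". The Finnish extract may therefore need widening.

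Finally, Table 4's row for severe mental disorders contains G35, the code that section 8 gives for MS. Applied literally to a register of MS hospitalisations, the list would code most of the cohort as yes. This is a sound warning about the remedy, and it applies equally to the Swedish and Norwegian use already planned.

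**Conclusion.** The point holds as an unexplained, avoidable gap in how an a priori confounder is measured in the country with the most planned pregnancies. That the register is omitted, is a study source and is not in the DPP follows directly from the text. That some hospital diagnoses are missed, and that their capture depends partly on the pregnancy's ending in Finnish terminations, follows from how the registers are described.

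The numerical effect is probably small: a few percent at most on the RR within Finland, and less when pooled. That range rests wholly on assumed prevalence, imbalance, disease effect and capture. The Protocol does not support a claim that Finnish capture is low, that the bias has a known sign, or that the primary conclusion is in danger. Planned size and power are unaffected. The change is worth making because it is cheap, not because the expected bias is large.

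**What to change.** In section 9.4, change the source entry to Patient Register (FIN, SWE, NOR), or state why Finland is left out. Remove G35 from the Table 4 code list. Then apply the codes to diagnoses before LMP by the same rule in all three countries and for all pregnancy outcomes. Where LMP is unavailable, use the proxy index date in section 9.2.4. State that look-back is limited to each register's available period, with Norway from 2008, so that the remaining difference is visible.

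The cost is a wider diagnosis code list in the Finnish extract. Section 6 places the permit applications one month after registration, so it can go into the first application. A rule confined to diagnoses before LMP also means that the row for pregnancy-related disorders (O10–O29) counts only from earlier pregnancies; the definition should say so.

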**Table 4: List of chronic diseases diagnosed before LMP and during pregnancy.**

Comorbidities	ICD-10	Proportion of women with the disease among parturient (%) in Finland 1996-2010 
Asthma and related conditions	E84.0, J41–J45, P27.1	2.77
Hypothyroidism (thyroid insufficiency)	C73, E03, E89.0	0.82
Epilepsy	C71, G40, G41	0.80
Rheumatoid arthritis and related conditions	A04.6, A39.8, A50.5, D76.0, D76.3, H20.1, H30, I33.0, J84, K50.9, K51.9, K73.2, K74.3, K83.0, L40.5, M02, M05, M06, M08, M13.9, M30–M35, M45, M46.1, M46.9, M94.1, N03, Q44.2	0.61
Diabetes Mellitus (type I and type II will be considered separately)	E10–E14, E89.1	0.52
Colitis Ulcerosa, Crohn's disease	K50, K51	0.50
Hypertensive diseases	I10–I13, I15, I27.0	0.38
Severe psychosis and other severe mental disorders and related conditions	A52.1, A69.2, A81.0, B22.0, B56.9, B57.2, E01.8, E03.9, E52, E53.8, E75.6, E83.0, E83.5, F01, F03, F06.0–F06.3, F20–F25, F28, F29, F30.1, F30.2, F31, F32.3, F33.3, F84, G10, G20, G30.0, G30.1, G30.8, G30.9, G31.0, G35, G40.9, M30.0, M32.8	0.32
Leukaemia and related conditions	C81–C85, C88, C90–C96, D45–D47, D72.1, D75	0.06
Hypercholesterolemia and mixed hyperlipidemia	E78.0, E78.2	0.05
Hypogonadism	E28.3, E29.1, E89.4, E89.5, Q96, Q98	0.04
Hypertensive heart disease with heart failure and related conditions	I11.0, I13, I50, I97.1, P29.0	0.04
Chronic arrhythmia of the heart	I47–I49	0.04
Glaucoma	H40	0.03
Pernicious anemia and deficiency of specified B group vitamins	C16, D51, E53.8	0.03

Comorbidities	ICD-10	Proportion of women with the disease among parturient (%) in Finland 1996-2010 
Hypothyroidism parathyroid gland, chronic (parathyroid insufficiency)	E20, E31.0, E89.2	0.02
Deficiency of coagulation, hemophilia	D66, D67, D68.0–D68.2	0.01
Myasthenia gravis	G70.0	0.01
Maternal pregnancy-related disorders	O10-O29	not available from DPP
Other malignancies	C00-C80	not available

Lahesmaa-Korpinen et al. 2014

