## 8 Research questions and objectives

This study is a population-based cohort study based on register data from three Nordic countries: FIN, SWE and NOR. The overall research questions of this study are to determine if exposure to IFN- $\beta$  before or during pregnancy has an adverse effect on pregnancy outcomes in patients with MS (ICD-10 G35) and, as requested by the CHMP, to identify the prevalence of adverse pregnancy outcomes in MS women unexposed to IFN- $\beta$  products. The cohorts from this study will provide background prevalence information and context for pregnancy outcomes in MS for the European IFN- $\beta$  Pregnancy Registry. However, the estimated prevalence from this study will not be directly compared with those from the European IFN- $\beta$  Pregnancy Registry as: First, available information on disease severity and other confounding factors differs between the health registers and the European IFN- $\beta$  Pregnancy Registry and in some cases is missing, such that the rates cannot be adjusted to be comparable. Secondly, the pregnancy cases included in the Nordic health registers are population-wide and are not based on a sample, whereas the European IFN- $\beta$  Pregnancy Registry is based on spontaneous reports.

The prevalence of the various pregnancy outcomes will be estimated in the study cohorts described below and in Table 1 (see section 9.4 for definition of exposure):

1. Women with MS exposed to IFN- $\beta$  only (i.e. these women have not been exposed to other MSDMDs) before or during pregnancy (cohort 1),
2. Women with MS exposed to IFN- $\beta$  regardless of exposure to other MSDMDs before or during pregnancy (cohort 2),
3. Women with MS unexposed to any MSDMD before or during pregnancy (cohort 3),
4. Women with MS unexposed to IFN- $\beta$  regardless of exposure to other MSDMDs before or during pregnancy (cohort 4),
5. Women exposed to MSDMDs except IFN- $\beta$  or glatiramer acetate (Copaxone®) or dimethyl fumarate (Tecfidera®) (cohort 5),
6. Women from the general population in FIN, SWE and NOR without MS diagnosis (cohort 6).

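### The any-chronic-diseases covariate counts MS itself (G35) as a comorbidity, so as written it cannot adjust for comorbidity, and its time window contradicts itself

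*Protocol*

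**What the plan says.** Section 8 states the study disease with its code: "adverse effect on pregnancy outcomes in patients with MS (ICD-10 G35". Section 9.4, under chronic diseases, says that the conditions in Table 4 are those "existing before, or during pregnancy will be identified based on diagnoses or specific medications for chronic diseases", and then: "From these comorbidities a binary variable will be created to indicate if the mother has had any chronic diseases before or during pregnancy". The look-back is lifetime, as far as the sources reach, and the MS Register is one of the sources.

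The row of Table 4 for severe psychosis and related conditions ends with the codes "G30.8, G30.9, G31.0, G35, G40.9, M30.0, M32.8". A later row, "Maternal pregnancy-related disorders", adds O10-O29.

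On timing, the same paragraph of Section 9.4 also says "Information is based on pre-pregnancy diagnoses", whereas the title of Table 4 and the variable list in Section 9.7.1 both include the pregnancy itself.

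The covariate is one of six variables forced into the base model for objective 2 (Section 9.7.3). It is also a candidate for the adjusted model, a cohort descriptor (Section 9.7.1) and a stratifier for objective 5 (Sections 8 and 9.7.4).

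**The concern.** All women in cohorts 1 to 5 have MS. If an MS code is enough to set the covariate to Yes, it no longer separates women with diabetes, epilepsy or hypertension from women without. The report would state that the primary comparisons were adjusted for chronic disease when no such adjustment had been made, and the chronic-disease strata of objective 5 would be empty on one side.

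The time window is a second, independent problem. A confounder for a drug exposure should be fixed before that exposure can act. Section 9.4 counts IFN-β purchases from six months before LMP, so an O10-O29 disorder coded in the index pregnancy can arise after exposure has begun. The chance of receiving such a code also grows with the length of the pregnancy, and TOPFA, a component of the primary composite, ends pregnancies early.

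**Working it through.** **1. The rule applied to a woman with MS.** Section 8 gives MS as G35. Table 4 contains G35. Section 9.4 sets the covariate to Yes for any Table 4 condition, with lifetime look-back. Nowhere is the index disease excluded. A woman with G35 recorded before or during the pregnancy is therefore Yes, whatever else she has.

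**2. Effect on the model.** Take three columns: intercept, exposure and the covariate, with 294 pregnancies in cohort 1 and 1270 in cohort 3 (Section 9.5).
- G35 included and MS on record for all: the covariate is 1 throughout, with variance 0. It equals the intercept column, the rank is 2 of 3, and its coefficient cannot be estimated. The univariate Wald screen in step 1 of Section 9.7.3 cannot be computed for it either.
- Covariate at 7.05% prevalence (simulated): it varies and the rank is 3 of 3.

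**3. How common the intended covariate would be.** Eighteen rows of Table 4 carry a proportion among Finnish parturients, 1996-2010:

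2.77 + 0.82 + 0.80 + 0.61 + 0.52 + 0.50 + 0.38 + 0.32 + 0.06 + 0.05 + 3×0.04 + 2×0.03 + 0.02 + 2×0.01 = 7.05%.

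This is an upper bound for those rows. A woman can be in several, and some codes are listed twice (for example G40.9, E03.9, E53.8, M30.0 and M32.8). O10-O29 and other malignancies have no figure. The figures are for Finnish parturients, not for women with MS.

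**4. If some women were diagnosed with MS after the pregnancy.** Let d be the share of cohort 3 so diagnosed, and let 7.05% of them have another listed condition. Then Yes in cohort 3 = 1 − d×(1 − 0.0705). The protocol does not give d. Over an assumed range:
- d = 5%: 1 − 0.05×0.9295 = 95%
- d = 30%: 1 − 0.30×0.9295 = 72%

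Cohort 1 stays at about 100%, because an IFN-β purchase in the exposure window implies that MS was already known. The covariate would then follow exposure and the date of diagnosis, not comorbidity.

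**5. What missing adjustment could do (illustration on assumed inputs).** With no drug effect, comorbidity prevalence q in cohort 1 and 7.05% in cohort 3, and a comorbidity risk ratio r for the outcome, the spurious RR is [1 + q(r − 1)] / [1 + 0.0705(r − 1)].
- q = 10%, r = 1.5: 1.050/1.035 = 1.01
- q = 20%, r = 3: 1.400/1.141 = 1.23

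The protocol gives neither q nor r, so this range is not an estimate.

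**6. The protocol's power figure.** With 294 against 1270, a baseline of 24/331 and a two-sided 5% level, RR 1.72 gives p1 = 1.72 × 0.0725 = 0.1247. The standard error is 0.0178 under the null (pooled) and 0.0206 under the alternative. Then z = (0.0522 − 1.96×0.0178)/0.0206 = 0.84, or 80% power. The stated 1.72 is reproduced. It is an unadjusted calculation, so the covariate does not touch it.

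**7. The time windows side by side.** Before or during pregnancy: the identification sentence and the yes/no sentence in Section 9.4, the Table 4 title, and Section 9.7.1. Pre-pregnancy only: the sentence "Information is based on pre-pregnancy diagnoses" in Section 9.4. Both cannot govern the same variable.

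**The case against.** A reader might infer that the covariate is Yes for every woman in the study. The protocol does not support that. Sections 9.2.1 and 9.2.2 do not require MS to be on record before the index pregnancy. Under the pre-pregnancy window, a woman first diagnosed after LMP and without another listed condition is No.

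The Finnish data add uncertainty. Finland supplies an estimated 777 of 1671 pregnancies (46%). For this covariate Section 9.4 names the Patient Register for Sweden and Norway only, and Section 9.3.1.1 describes MS registers only in those two countries. Finnish disease status in the DPP comes from special-reimbursement entitlement, and whether an MS entitlement would set the psychosis row is not stated. This limits certainty without rescuing the variable: if G35 worked only in Sweden and Norway, the covariate would mainly repeat the country term already in the base model.

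The word comorbidities normally excludes the index disease, and G35 in a mental-disorder row looks like a list carried over unedited. That explains the error, but the code list is the written definition. The 0.32% shown for the row describes all Finnish parturients, not women with MS.

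A second tempting reading is that O10-O29 codes can come only from the index pregnancy, so that the covariate is partly caused by the outcome. Section 9.7.1 lets one woman contribute several pregnancies and Section 9.4 looks back over a lifetime, so a code from an earlier pregnancy is a legitimate pre-LMP diagnosis. The post-exposure problem exists only if the window that includes pregnancy governs. The entry for O10-O29 in the proportion column says only that the DPP has no figure; it does not remove the codes.

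Finally, a constant column would show in the Section 9.7.1 tables and would drop out rather than distort the estimate. That is fair, but a prespecified confounder of the primary model would then be redefined after the data had been seen.

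**Conclusion.** The concern holds in this form. Table 4 puts the study disease among the codes that define chronic comorbidity. As written, the covariate is constant for women whose MS was recorded before or during the pregnancy in the sources used, and otherwise marks when MS was diagnosed. In neither case does it adjust for comorbidity, although it is forced into the base model and used as a stratifier.

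The intended variable would be Yes for at most 7.05% of Finnish parturients on the rows with a figure; its prevalence in women with MS is not given. No bias of known size in the primary RR follows, since the range of 1.01 to 1.23 rests wholly on assumed inputs. The study-size figures stand.

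The conflict of time windows is real and separate. Its consequence for O10-O29 is conditional on the window that includes pregnancy.

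**What to change.** - Delete G35 from the codes that define the any-chronic-diseases covariate.
- Restrict the covariate to diagnoses or medications recorded before LMP. This is a choice between two stated windows and not just a clarification, so it must be carried through the identification sentence and the yes/no sentence in Section 9.4, the Table 4 title and the Section 9.7.1 list.
- Keep O10-O29 codes from the index pregnancy out of the confounder. Codes from earlier pregnancies may stay in or be reported descriptively.

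The cost is one code removed and a handful of wording changes, made before data are analysed. No new data, no change to the cohorts and no change to the power calculation are needed.
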